20.0	Compensation for Research-Related Injury	14
21.0	Economic Burden to Subjects	14
22.0	Consent Process.....	14
23.0	Process to Document Consent in Writing.....	17
24.0	Setting	18
25.0	Resources Available	18
26.0	Multi-Site Research*	19

PROTOCOL TITLE: EHR Embedded Comparative Effectiveness Studies

Study Summary

Study Title	EHR Embedded Comparative Effectiveness Study
Study Design	Survey and interview assessment of parallel group randomization embedded into clinical processes and EHR Systems
Primary Objective	Evaluation of the feasibility, quality, and acceptability of informatics systems and consent procedures for EHR embedded comparative effectiveness research.
Secondary Objective(s)	
Research Intervention(s)/Investigational Agent(s)	The demonstration interventions are: Initial visit with Dietitian (RD) then Health Coach (HC) or initial visit with Health Coach (HC) then Dietitian (RD) in Weight & Wellness Center (WWC); and activity restriction versus activity as tolerated post discectomy (see below for full descriptions)
IND/IDE #	N/A
Study Population	1) Patients and providers in the D-H Weight & Wellness Center (WWC) of the Department of Medicine enrolling in obesity management programs; 2) patients undergoing spine surgery for disc herniation in the DH Center for Pain and Spine (CPS).
Sample Size	For the WWC: 30 for RD then HC initial visit, 30 for HC then RD initial visit; For the CPS: 30 for activity restriction/30 for activity as tolerated.
Study Duration for individual participants	6 months of follow-up for CPS patients; follow-up for WWC patients is dependent on when the intervention was completed which could range from 1-6 months.
Study Specific Abbreviations/Definitions	Health Coach (HC); Registered Dietitian (RD) Weight and Wellness Clinic (WWC); Dartmouth Hitchcock Medical Center (DHMC); Center for Pain and Spine (CPS)

PROTOCOL TITLE: EHR Embedded Comparative Effectiveness Studies

Objectives*

- Evaluation of the feasibility, ease of use, quality, and acceptability of informatics systems and consent procedures for EHR embedded comparative effectiveness research.
- Estimate survey-based patient-participation, approval of EHR processes, and assigned treatment completion rates for embedded randomization procedures in the Weight and Wellness Clinic comparing visit order for initial Health Coach (HC) and Registered Dietitian (RD) visits (part of initial WWC multidisciplinary evaluation at approximately 2 weeks).

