Initial pilot testing will take place at each demonstration center. Clinicians and support staff will be trained in using the EPIC based systems and clinical workflows. This feedback will be used to make final revisions to the systems and procedures for the demonstrations as necessary.

All potentially eligible patients in demonstration protocols will be initially identified through EPIC system alerts. Alerts will be triggered by surgeon orders for discectomy in the CPS and by entering into the pathway order screen in the WWC.

If the clinicians confirm that eligibility criteria are met, the patients will be asked if they would consider participation in a research project. If the patient is in person and agrees, the demonstration protocol will be explained and information sheet will be handed out. If the patient is not in person the information sheet will be mailed or emailed out to the participant via RedCap link. They will be asked to consent to be assigned randomly to one of the comparative effectiveness interventions and to participate in the follow-up survey and potentially a follow up semi-structured interview (see below). This follow up survey may be done in person via paper survey, sent via RedCap link, or participants can answer the survey questions verbally over the phone and a research assistant will enter responses directly into RedCap.

The software will return a computer-generated treatment assignment, with random block sizes chosen to balance the number in each comparison group. A code will be stored in the patient record to indicate the assigned treatment. The provider will be notified of the assigned treatment and place the proper orders in EPIC. In the WWC, this will be done using the pre-defined pathway order screen in EPIC.

PROTOCOL TITLE: EHR Embedded Comparative Effectiveness Studies

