We will use a brief post-visit survey (<5 min) with all patients who are approached about participating in the two studies. The survey will focus on the consent process, reasons for deciding to consent or to not consent, and a few demographics (e.g., gender, age, race, education level). The survey will be anonymous and will be given to the patient at the end of their visit or after their consent phone call. This brief post-visit survey may be done in person via paper survey, sent via RedCap link, paper survey via mail, or participants can answer the survey questions verbally over the phone and a research assistant will enter responses directly into RedCap. Invitations to participate in the survey will be sent up to four times by mail or email,

For patients in the CPS who have decided to enroll we will use the sheets to also gather their contact information for possible interviewing. To allow us to get feedback from unenrolled patients, the information sheet will have a tear off section with blanks for the patient's contact information. That sheet will be torn off before being given to an unenrolled patient who will remain anonymous.

All the demonstration interventions are considered standard of care at DHMC. Risks will be monitored according to clinical standards as currently employed in the participating clinics.

A follow-up survey will be sent after 1 to 6 months to ask whether they received the assigned treatment, their perceptions of the study processes, and some basic demographic information. The survey and semi-structured interviews will be conducted by the Center for Program Design and Evaluation at Dartmouth (CPDE) and overseen by [name], study Co-I. Identifying information (e.g., name, email, address, phone number) will only be used to contact the participant and send them a survey or administer it by phone, and to assess their interest in being interviewed. Invitations to participate in the survey will be sent up to four times by mail or email, and paper surveys will be mailed as a last resort to non-respondents with a paid return envelope.

Participants who agree to be contacted for the semi-structured interview will be asked their preference for setting up an interview (e.g., by email or phone). CPDE staff will use the participant's preference to contact them to set up an interview time. All interviews will be conducted by phone, audio-recorded, and transcribed for analysis.

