Following study completion treatment status and patient reported outcomes determined through retrospective chart review based on EHR data.

Data and Specimen Banking*

PROTOCOL TITLE: EHR Embedded Comparative Effectiveness Studies

Study data are derived from responses to the surveys. Patient level data files will be maintained until a final report is released. Full name, email and phone number will be entered into RedCap database and will only be stored with the study team.

Sharing of Results with Subjects*

Summary results from the demonstrations will be available as a published final report from the funding agency (PCORI), and in scientific publications. Information on the location and timing of summary results will be communicated to participating patients during the consent process.

Study Timelines*

The anticipated start date for enrollment into the study is September 1, 2020. Approximately three months is expected for enrollment. Patients will be contacted 1-6 months following enrollment for follow-up surveys. The estimated date for completion of the last enrollment is December 1, 2020, with the last follow-up survey completed by March 1, 2021. The primary data analyses will be executed on a blinded basis as survey data are accrued, and summarized by the end of March.

PROTOCOL TITLE: EHR Embedded Comparative Effectiveness Studies

Inclusion and Exclusion Criteria*

CPS

Inclusion Criteria: Adults (>18) able to consent, with sufficient fluency in English; indications for discectomy; able to restrict activities or to resume activities as tolerated.

Exclusion Criteria: Pregnant women; Prisoners; Children (<18).

WWC

Inclusion Criteria: Adults (>18) able to consent, with sufficient fluency in English; initial RD and HC visits are part of routine care as recommended by the provider; willing to be randomized.

Exclusion Criteria: Pregnant women; Prisoners; Children (<18).

Vulnerable Populations*

N/A

Local Number of Subjects

WWC: 60 patients total, 30 in each treatment arm.

CPS: 60 patients total, 30 in each treatment arm.

Recruitment Methods

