The consent process may take place in person at the WWC, or over the phone, or via videoconference. The participant will be asked to provide their preferred email during this conversation or address if they do not have email or internet. Both phone and videoconference process will be standardized and involve using the script provided for the WWC for the initial RD and HC visit order. The information sheet will be emailed to the participant via a RedCap link or mailed if unable to be emailed.

In CPS for the post-discectomy Activity Restriction/Activity as Tolerated, following the SOP: Informed Consent Process for Research (HRP-090).

Process to Document Consent in Writing

Given the minimal risk, a waiver of documentation of written consent is requested for this protocol. Note that all data are collected via anonymous survey, and no HIPPA data are collected.

Note that both WWC and the CPS have reviewed and approved this protocol. Consent scripts are attached as well as a detailed information sheet for each comparison, covering all required consent elements.

A waiver of HIPPA authorization is requested for the retrospective use of EHR data and chart reviews for patients who are no longer participating in the study. The data are requested to assess the feasibility of our embedded systems and processes, and, as in other retrospective EHR chart reviews, it is not practicable to obtain consent. The privacy risks are mitigated by the use of deidentified analytic data sets, which are securely stored. The files linking the study IDs to patient records will be destroyed at the conclusion of the study. PHI will not be reused or disclosed following the conclusion of the study.

Setting

The study will be conducted in the Department of Medicine D-H Weight & Wellness Center Clinic and in the Department of Orthopedic Surgery Center for Pain and Spine. All interventions are standard of care and will be performed at these sites. The DH Research Ethics Committee serves as an advisory board and includes community representation.

Resources Available

There are approximately 150 patients per year/75 per 6 months who undergo lumbar discectomy at DHMC, of whom we plan to enter 30 to each of the two arms for activity restriction following discectomy.

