Current WWC volume is estimated at approximately 600 patients per year (300 during the randomization period of 6 months, with capacity for up to 30. We plan to enroll 30 in the RD then HC initial visit, 30 for HC then RD initial visit;

PROTOCOL TITLE: EHR Embedded Comparative Effectiveness Studies

The participating clinic investigators are all part of the research team and have been meeting multiple times per month since the beginning of the study to plan the procedures and informatics. The first two weeks of the accrual period will be used to conduct the testing and provide final guidance for the clinical staff.

The facilities used for conducting the research include the clinic sites, the Department of Biomedical Data Science, Divisions of Biostatistics and Biomedical Data Sciences, The Dartmouth Institute, and the D-H Analytics Institute. The project supports approximately 40% FTE for the Investigators and Co-Investigators and 120% FTE for staff in supporting roles as research assistants and programmers. Informed consent will be performed by clinic investigators and clinic assistants, most of whom are regular participants in team meetings. Scripts and training will be reviewed prior to initiation of the demonstration projects.

Multi-Site Research*

One of our Co-Investigators, [name], has moved to the University of North Carolina (UNC). To maintain his involvement in this and other of his studies at Geisel and at Dartmouth-Hitchcock, we have changed the designation of this trial to a multi-site trial, including UNC. The appropriate materials for this change were uploaded in MOD00011236.

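### The planned dates allow spine-surgery (CPS) patients at most 90 to 181 days from enrolment to the last survey, not the stated 6 months; the enrolment period is stated inconsistently and the survey is timed from enrolment rather than surgery

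*Combined protocol and SAP*

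**What the plan says.** **Follow-up length.** The Study Summary, under duration for individual participants, states "6 months of follow-up for CPS patients; follow-up for WWC patients is dependent on when the intervention was completed", and gives the 1 to 6 month range for WWC only. Study Timelines does not separate the two clinics: "Patients will be contacted 1-6 months following enrollment for follow-up surveys". Procedures Involved repeats the range without a start point: "A follow-up survey will be sent after 1 to 6 months to ask whether they received the assigned treatment".

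**Dates.** Study Timelines anticipates enrolment from September 1, 2020, over roughly three months. It continues: "The estimated date for completion of the last enrollment is December 1, 2020", "with the last follow-up survey completed by March 1, 2021". Analyses are to be summarised by the end of March.

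**Enrolment length and supply.** Resources Available describes WWC volume as "300 during the randomization period of 6 months". For CPS it says: "There are approximately 150 patients per year/75 per 6 months who undergo lumbar discectomy at DHMC". The CPS target is 60, 30 per arm.

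**Start point for CPS.** Procedures Involved says: "Alerts will be triggered by surgeon orders for discectomy in the CPS". Recruitment Methods names the same event and starts consent after eligibility is confirmed. Both CPS arms consist of post-operative instructions, and Arm A's bending, twisting and lifting limits are stated for 4 weeks.

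**Record outcomes.** For CPS, Study Endpoints adds treatment status and patient-reported outcomes taken retrospectively from the EHR where available. Data Management and Confidentiality requests these data, including surgery date and discharge instructions, after study completion, and puts completion at around March 2021.

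**The concern.** A reader of the Study Summary would expect each CPS patient to be followed for 6 months. The calendar in Study Timelines appears to give most of them much less. The two stated enrolment lengths make it worse: if CPS enrolment runs longer to reach its target while the last-survey date stays fixed, the latest patients lose still more follow-up.

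The start point matters for a different reason. The follow-up survey asks whether the assigned treatment was received, and for CPS that treatment begins at or after the operation. A clock that starts at enrolment, after the surgery order, does not guarantee that the operation has taken place when the patient replies. The Objectives call the quantity treatment completion and the precision table in Data Management and Confidentiality calls it adherence. Neither term is defined, so the plan does not say what a reply must cover to be valid.

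**Working it through.** **Inputs.** From Study Timelines: enrolment start September 1, 2020; last enrolment December 1, 2020; last survey March 1, 2021. From the Study Summary: 6 months of CPS follow-up and a CPS target of 60. From Resources Available: 150 discectomies a year, 75 per 6 months, and a 6-month randomization period (stated for WWC).

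**1. Reproduce the plan's enrolment period.** September 1 to December 1, 2020 = 30 + 31 + 30 = 91 days, which agrees with about three months. Counting both ends, there are 92 possible enrolment dates.

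**2. Longest time from enrolment to survey** = March 1, 2021 minus the enrolment date.
- Enrolled September 1: 91 + 90 = 181 days, exactly 6 calendar months.
- Enrolled December 1: 31 + 31 + 28 = 90 days, 3 calendar months.
- Six calendar months before March 1, 2021 is September 1, 2020, so 1 of 92 dates fits. If 6 months is read as 180 days, September 2 also fits, making 2 of 92.

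**3. CPS supply in the stated enrolment period.** 150 × 91/365 = 37.4 discectomies, against 60 planned, even if every patient enrols.
- Shortest time to reach 60: 60/150 × 365 = 146 days, that is January 25, 2021. This leaves 181 − 146 = 35 days to the last-survey date.
- Over 6 months: 60/75 = 80% of patients would need to enrol. The target therefore fits a 6-month supply and not a three-month one.
- Six months from September 1 ends on March 1, 2021, the last-survey date itself, leaving 0 days for a patient enrolled at the end.

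**4. What 6 months for everyone would need.** December 1, 2020 plus 6 months is June 1, 2021. That is 30 + 31 + 31 = 92 days after March 1.

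**5. Start point.** Let *d* be the days from enrolment to surgery. The documents do not give it; 7 to 42 days is assumed here only to show the range. Taking one month as 30 days, a survey at the opening of the window falls on post-operative day 30 − *d*.

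| *d* (assumed) | Earliest survey, relative to surgery | Longest post-surgery time, first and last enrollee |
|---|---|---|
| 7 | day 23 | 174 and 83 days |
| 28 | day 2 | 153 and 62 days |
| 42 | 12 days before surgery | 139 and 48 days |

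The last column is 181 − *d* and 90 − *d*.

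**The case against.** **The dates are only anticipated or estimated, and 1 to 6 months is a workable window.** Both are true. A December 1 enrollee can be surveyed between January 1 and March 1. But an enrolment period of three months followed by three more to the last survey cannot give everyone 6 months, whatever the start date. Later enrolment with the same last-survey date shortens follow-up further.

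**The 6 months may refer to record outcomes.** The Study Summary does not say that its 6 months means survey follow-up, and Study Endpoints adds retrospective outcomes for CPS alone. The reading is plausible but nowhere confirmed. Those outcomes have no time point or cut-off, study completion is put at around March 2021, and the files linking study IDs to records are to be destroyed at the study's conclusion.

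**No objective uses a 6-month time point.** This stands. A reader might infer that a primary 6-month endpoint is lost. The objectives concern participation, approval and treatment completion, so that inference is not supported.

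**The 6-month randomization period is stated for WWC.** Also correct. For CPS, 75 per 6 months is a volume. That CPS enrolment was meant to last 6 months is suggested by the arithmetic but not stated.

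**The start-point problem is conditional.** A reader might infer that early surveys will misclassify Arm A replies by a known amount. The documents do not support that. It would need surveys sent as the window opens, a sufficient but unstated gap before surgery, and completion meaning that 4 weeks of limits were followed. The plan leans towards instructions received: the arms are defined as instructions, the survey asks about receipt, and treatment status is verified from discharge instructions. Up to four invitations, and gift cards described as for end-of-study surveys, also suggest that many replies could come later.

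**Conclusion.** The point holds as an internal inconsistency in duration and enrolment, with a smaller gap in the survey's start point. On the stated dates, CPS survey follow-up can reach at most 181 days for the first enrollee and 90 for the last. Six months is open to 1 of 92 enrolment dates (2 if counted as 180 days). These are maxima on estimated dates, not forecasts of observed follow-up. For CPS, 90 days is optimistic for the last patient, because three months supplies about 37 discectomies against 60 planned; this assumes that 150 a year arrive evenly.

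The start point is a gap to close, not a demonstrated bias. Nothing in the plan prevents a treatment-received reply before surgery, but the number of such replies cannot be estimated without the order-to-surgery interval. If completion means instructions received, any post-operative reply is sufficient. If it means the stated 4-week period was completed, replies dated earlier cannot establish it.

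**What to change.** 1. Reconcile the Study Summary, Study Timelines and Resources Available into one enrolment period that can supply 60 CPS patients, and one CPS follow-up length. There are two routes:
   - Restate CPS survey follow-up as up to about 3 to 6 months from enrolment on the current dates, with 6-month EHR outcomes as available. This is a wording change, but the 3-month lower end holds only if enrolment closes on December 1.
   - Keep 6 months and move the last survey to at least 6 months after the last CPS enrolment. For a December 1 enrollee that is June 1, 2021, a delay of 92 days that also takes the survey past the end-of-March summary.
2. Time the CPS survey from the surgery date, or record that date on the survey, so that no treatment-received reply is collected before surgery. This costs one added item, or access to the surgery date earlier than the post-completion data request, with the approval that either needs. The last-survey date may also have to move.
3. State whether *completion* and *adherence* mean instructions received or the stated 4-week period completed. If the latter, count only replies dated after that period. The definition costs nothing; the restriction may reduce the number of usable replies.

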Hypothesis: Patients participation and approval rates of the process will be greater than 80%.
- Estimate survey-based patient-participation, approval of EHR processes, and assigned treatment completion rates for embedded randomization procedures in the Center for Pain and Spine comparing activity restriction versus activity as tolerated following discectomy in the Center for Pain and Spine (CPS).
Hypothesis: Patients participation and approval rates of the process will be greater than 80%.
Following study completion, verify treatment status and determine EHR outcomes through chart review and records from the D-H data warehouse.

Background*

It is commonly acknowledged that patient-clinician decision making is inadequately supported by evidence on the comparative effectiveness of alternative therapies. In response to this need, efforts to reform health care delivery—such as the Affordable Care Act—have included large investments in improving electronic health record systems (EHR) as a potential source of evidence development. The expectation is that the large quantity of organized and accessible health care records will ultimately provide a resource for conducting comparative effectiveness research on an ongoing basis to guide “learning health care systems.” [IOM (Institute of Medicine). Digital Data Improvement Priorities for Continuous Learning in Health and Health Care: Workshop summary. Washington, D.C.: The National Academies Press; 2013.]

This protocol will evaluate the feasibility, quality, and acceptability of informatics systems and consent procedures for EHR embedded comparative effectiveness research based in eDH, our Dartmouth-Hitchcock EHR.

Two initial demonstrations evaluating the new systems will be conducted targeting obesity interventions in the D-H Weight & Wellness Center (WWC): initial visits with

PROTOCOL TITLE: EHR Embedded Comparative Effectiveness Studies

Dietitian (RD) then Health Coach (HC) or initial visits with Health Coach (HC) then Dietitian (RD); and in the CPS: activity restriction versus activity as tolerated following discectomy.

In the WWC, the demonstration will focus on patients who are returning for their RD and HC visit. These visits are scheduled after the initial provider visit. These visits are a part of normal clinical care and are scheduled interchangeably as part of the initial WWC multidisciplinary evaluation.

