In spine surgery, patients undergoing lumbar discectomy commonly have post-operative restrictions related to bending, twisting, and lifting, as well as return to work. However, it is also common to have these activities allowed as tolerated [Carragee EJ, Helms E, O'Sullivan GS. Spine;1996;21(16):1893-1897], and both approaches are used in the DHMC Center for Pain and Spine.

Study Endpoints*

WWC: System recorded activity and patient surveys/interviews for the quality, and acceptability of informatics systems and consent procedures.

CPS: System recorded activity and patient surveys/interviews for the quality, and acceptability of informatics systems and consent procedures. Treatment status and patient reported outcomes as available retrospectively in the EHR.

Study Intervention/Investigational Agent

In the WWC obesity and related complications are managed by a WWC provider and obesity specific medications are prescribed as needed. Team care is provided by dietitians and health coaches. Progress is monitored at provider visits every 1-3 months with an aim to provide skills and support for sustained lifestyle change with a goal of 5-10% weight loss. Due to the COVID19 pandemic visits are now offered as a hybrid of in-person and telehealth visits.

In the WWC, the demonstration will focus on patients eligible and willing to be randomized for the order of their initial RD and HC visits. Both visits are offered as part of routine clinical care following the first provider visit and are consistent with current best practice medical guidelines for obesity.

WWC Arm A: Scheduling the initial RD visit first and then the HC visit as part of standard care.

PROTOCOL TITLE: EHR Embedded Comparative Effectiveness Studies

WWC Arm B: Scheduling the initial HC visit first and then RD visit as part of standard care.

CPS Arm A: Standard post-operative activity instructions (i.e., no bending, twisting, or lifting more than 10 lbs for 4 weeks, no return to work until cleared to do so).

CPS Arm B: Instructions advising activity as tolerated and return to work based on patient discretion

Procedures Involved*

The software will identify patients for consent and randomized treatment assignments in obesity treatment and spine surgery. Eligible patients will be identified and approached during patient visits to consent for participation.

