Patients will be identified during clinic visits using pre-defined events recorded in the EHR. For WWC, the identifying event will be entering into the program order entry program during the second clinic visit for patients enrolling in obesity pathways. For the CPS, the identifying event will be the surgeon ordering discectomy. Following confirmation of eligibility criteria, recruitment and consent process will be initiated.

Risk descriptions will be provided for both the standard of care options in the WWC and CPS according to established clinical practice.

Withdrawal of Subjects*

It is unlikely that patients will be withdrawn unless the study terminates prematurely. In this case, participating patients and providers will be notified. Partial withdrawal from procedures will not affect the continued data collection, unless the patient also withdraws permission to use their data. No plans are in place to collect survival data.

Risks to Subjects*

PROTOCOL TITLE: EHR Embedded Comparative Effectiveness Studies

No clinical risks beyond those of standard of care treatment are anticipated. Patients will be informed of these risks according to currently used procedures in the clinics and during the consent process. Patients will be contacted for follow-up questionnaires, and risks/protections regarding privacy will be discussed in the consent process.

Potential Benefits to Subjects*

There are no direct benefits.

Data Management and Confidentiality*

Data collected through the surveys and interviews will be subject to strict confidentiality safeguards. The brief post-visit survey and follow up survey may be conducted using DH RedCap account, which is a standard and secure online survey platform. Interview audio recordings will be transcribed and analyzed; the audio will be destroyed at the completion of the full study (around March 2021). In addition, the following procedures will be used to minimize risk: 1) unique identifiers will be assigned to each participant, and any potential identifiers (e.g., name) in surveys or transcripts will be removed prior to entering data into software for analysis; and 2) only the members of the study team will have access to a list linking unique IDs to participants; this list will be stored on a password protected computer. Information will be kept on password-protected secure computers and electronic files.

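### Could the weight-clinic trigger at an undefined second clinic visit put random assignment after the dietitian and health-coach visit order is already fixed?

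*Combined protocol and SAP*

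**What the plan says.** Five sections of the combined protocol and SAP bear on WWC timing.

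- **Recruitment Methods**: "the identifying event will be entering into the program order entry program during the second clinic visit for patients enrolling in obesity pathways". Consent follows confirmation of eligibility. The visit is not defined here or elsewhere.
- **Procedures Involved**: the alert is triggered "by entering into the pathway order screen in the WWC", with no visit number. After eligibility, consent and computer-generated assignment, "The provider will be notified of the assigned treatment and place the proper orders in EPIC"; for the WWC, the pathway order screen is named as the place where this is done.
- **Background**: "These visits are scheduled after the initial provider visit", and "the demonstration will focus on patients who are returning for their RD and HC visit".
- **Objectives**: the RD and HC visits are "part of initial WWC multidisciplinary evaluation at approximately 2 weeks". The starting point of the 2 weeks is not given.
- **Study Intervention/Investigational Agent**: "Both visits are offered as part of routine clinical care following the first provider visit". The arms are defined by which of the two visits is scheduled first. The section also says "Progress is monitored at provider visits every 1-3 months".

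The assigned-treatment completion rate is a stated WWC objective. Data Management and Confidentiality requests the assignment date and the dates of the initial HC and RD visits. No section says how to count a patient whose visit order was fixed before assignment.

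**The concern.** Read in isolation, the trigger sentence can be placed after the event it is meant to govern. If the second clinic visit is the second provider visit, and provider visits are 1-3 months apart, the alert fires well after RD and HC visits held at about 2 weeks. If it is the return visit for the RD or HC, the first of the pair is already settled. In both cases the software would randomize an order that already exists.

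The completion rate would then lose its meaning for those patients. With two possible orders and 1:1 assignment, about half would match their assigned arm by luck. Counting the matches as completion would credit the embedded system with something it did not do, and would hide a workflow failure that a feasibility study exists to find. The WWC inclusion criteria do not close this off: they do not require that the RD and HC visits be still unbooked.

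**Working it through.** **1. The plan's own precision figures.** Data Management and Confidentiality gives 90% CI half-widths of 13%, 15% and 16% for rates of 80%, 70% and 60% with N = 30 per arm. Exact (Clopper-Pearson) intervals at 24, 21 and 18 of 30 have half-widths of 13.3%, 14.9% and 15.8%, which round to the stated values. The table is sound and is the yardstick for size. For all 60 WWC patients together, the exact half-widths are 9.2%, 10.4% and 11.1%.

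**2. What late assignment would do.** Let f be the share assigned after the order was fixed and not rebooked, c the completion rate among those assigned in time, and q the share with RD first beforehand.

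- Chance agreement under 1:1 assignment: 0.5q + 0.5(1 − q) = 0.50 for any q.
- Observed completion: c(1 − f) + 0.5f.
- Completion delivered by the system: c(1 − f).
- Overstatement: 0.5f, whatever c is.

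At f = 0 the overstatement is 0; at f = 0.25 it is 12.5 points; at f = 0.50 it is 25 points. To equal the 9.2-point half-width for 60 patients at an 80% rate, f would have to be 0.092/0.5 = 0.184, or about 11 of 60 patients. The arithmetic is right, but no section gives a value for f.

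**3. Whether the documents support f above zero.** Three readings of the second clinic visit can be set against the other sections.

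| Reading | Needs | Fit with the rest of the plan |
|---|---|---|
| Second provider visit, at 1-3 months | The monitoring interval applied to the initial evaluation, and the 2 weeks counted from the first provider visit | Poor. The interval describes ongoing progress checks, and the origin of the 2 weeks is not stated. Patients would have no initial visit order left to randomize |
| RD or HC return visit | The alert firing once the first of the pair is booked or under way | Poor. The alert is tied to the order screen, and orders follow assignment |
| An encounter at which the RD and HC visits are ordered | Nothing further | Good. It agrees with the sequence of alert, consent, assignment, orders |

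The deciding point is in Procedures Involved. In the WWC the screen that triggers the alert is also the screen on which the provider places orders after learning the assignment. Recruitment Methods names the same event, order entry, and adds a visit number as a description. Study Intervention then defines the arms by scheduling one visit ahead of the other, which presupposes that scheduling is still open. Late assignment therefore requires RD or HC visits to be booked outside or ahead of the pathway screen. No section says that this happens.

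**4. Checks already planned.** Procedures Involved provides for pilot testing at each center, with revisions before the demonstrations. Resources Available sets aside the first two weeks of accrual for testing. Treatment status is verified by chart review, and the requested assignment and visit dates would show any assignment made after a visit.

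**The case for a change.** The best argument for a change is that Procedures Involved shows intent without naming a visit, so it does not by itself correct Recruitment Methods. Consent may also be taken by phone or video, so assignment need not fall in the encounter that raised the alert. Background adds that RD and HC visits are booked interchangeably in routine care, so a patient could hold a booking before any assignment. And the treatment of even a few such patients moves the rate. With 3 of 30 in an arm assigned late and an assumed 80% completion among the other 27 (0.8 × 27 = 21.6), the arm's rate is 21.6/30 = 72% if the three count as failures, (21.6 + 1.5)/30 = 77% if half match, and (21.6 + 3)/30 = 82% if all count as completed.

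Part of this stands. The term is undefined, the sections would read better if they named the same encounter, and no counting rule is written. The requested dates also cover visits and not bookings, so they cannot show every late assignment.

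The rest does not carry. Remote consent delays assignment, but in the written sequence the orders still wait for it. A visit booked but not yet held can be rebooked, and then the chance-agreement argument does not apply. Counting concordant late patients as failures would be a change of outcome: the plan asks whether the assigned treatment was received, and a patient seen in the assigned order did receive it. Whether the system caused that order is a different, arguable quantity.

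**Conclusion.** No change to the plan follows. The second clinic visit is an undefined label, but the written sequence puts assignment before the orders, and the arms are defined by scheduling that comes afterwards. Under that sequence the late share, and with it the overstatement of 0.5f, is zero. A material effect, of the order of the plan's own half-widths, would need roughly a fifth of WWC patients to be assigned late with their order left as it was. The documents offer no sign of this.

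The conclusion assumes that the clinic runs the order screen as Procedures Involved describes. If it does not, the planned pilot is where that should surface, and the assignment and visit dates allow a descriptive count of patients assigned on or after the earlier visit without any new data. An analyst would sensibly keep every randomized patient in the denominator and mention any such cases. The consent scripts and information sheets are said to be attached but are not among the pages available, so they may state the timing more exactly. This is a matter of wording, and no planned result is shown to be wrong.
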